Overview. Patients included in the study will be female and male survivors of intentional and unintentional injuries ages ≥ 18 , who speak English and are admitted to the University of Washington's Harborview Level I Trauma Center inpatient surgical ward or emergency department for ≥ 24 hours. All injured patients will undergo electronic health record screening for high levels of emotional distress. A previously developed electronic medical record screen will be used to assess the population of admitted injured trauma survivors at risk for the development of PTSD.⁹¹ The screen utilizes 10 data elements that are both associated with increased risk for PTSD and that are readily available in any robust EMR system; patients with ≥ 3 risk domains positive will be approached for informed consent. (see also Appendix). When the 10 data elements were used to predict scores on the PTSD Checklist of ≥ 35 , the electronic medical record screen demonstrated adequate sensitivity (0.71), specificity (0.66), and area under the ROC curve (0.72).⁹¹

Inclusion Criteria. Patients determined to be at risk on the electronic health record screen will be approached for informed consent. After informed consent is obtained, patients will be screened for emotional distress; patients who score ≥ 35 on the PTSD checklist and endorse ≥ 1 severe posttraumatic concern will be randomized into the longitudinal portion of the investigation.^{47,67,71} Prior to randomization, all patients will complete the full baseline assessment.

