The study team will use mixed effects regression models to test these hypotheses for both continuous and discrete outcomes.¹²⁸⁻¹³¹ The investigative group has extensive experience with this analytic approach in the analyses of longitudinal data after injury.^{20,24,47,67,68,71} In addition, these models will allow the use of covariates that model potential sources of non-response bias and time-dependent covariates. This type of model also allows the specification of random or fixed effects and the form of the serial correlation over time (if heterogeneity changes over time).

The effect of major interest will be the time by treatment group interaction term. For these models, repeated measurements of the baseline, 1-, 3-, 6-, 9-, and 12-month outcome assessments (i.e., EDIE documented emergency department utilization, concern severity, PTSD Checklist and MOS SF-36 Physical Components Summary (PCS) scale scores) will be the dependent variables. For all dependent variables, the study team will first fit models containing only time categories, intervention, and intervention by time interactions. The form of the dependent variables will determine the link function used.

The impact of including covariates in the model will be examined in planned sensitivity analyses (IR-5). As in prior study team investigation, sensitivity analyses will be used to assess the impact of key assumptions. Important injury and demographic characteristics, such as Injury Severity Score and age, will be entered into the models as covariates in planned sensitivity analyses. Prior to these analyses, the study team will examine baseline treatment group differences, using the appropriate statistics for the distribution of the variable. Although randomization should ensure balance between the two groups, it is essential to control for any known confounders in the design and analysis to prevent a biased assessment of the treatment effect. Any baseline injury, demographic, or clinical variables found to be statistically significant in this analysis will also be included as covariates in the regression models. Care processes will also be examined as part of the secondary data analytic plan.

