i. Emergency Department Utilization. The primary health care system intervention target will be group differences in emergency department utilization. In the prior PCORI funded investigation, at 3-6 months post-injury, 30% of nurse notification patients versus 17% of care management patients had one or more emergency department visits (13% difference across groups), at 6-9 months post-injury, the differences were 31% nurse notification versus 21% care management (10% difference across groups), and at 12 months post-injury, the differences were 30% nurse notification

versus 22% care management (8% difference across groups).⁴⁷ With the 100% follow-up rate provided by EDIE, the probability of a 2-tailed type I error set at 5%, correlation between observations of 0.7, and a similar pattern of emergency department visits as seen in the prior PCORI investigation with 424 total patients (n = 212 in each arm), the power is ≥ 0.80 .

ii. Severity of posttraumatic concerns. In the prior PCORI investigation, at the six month post-injury time point, 74% of nurse notification patients endorsed 1 or more severe concerns versus 52% of care management patients at the six month post-injury study endpoint, for a 22% absolute difference between the two groups.⁴⁷ For patient-reported outcomes such as the endorsement of one or more severe posttraumatic concern, 20% 12-month attrition is anticipated. With 20% 12-month attrition, 424 patients, the probability of a 2-tailed type I error set at 5%, correlation between observations of 0.7 and a similar pattern of endpoint posttraumatic concern reduction as seen in the prior PCORI investigation (22% reduction in the endorsement of any severe post-injury concern), the power to detect differences in posttraumatic concern severity will be ≥ 0.80 .

iii. PTSD symptoms. In prior comparative effectiveness trials conducted by the study team, at the 12-month time point, collaborative care patients demonstrated a mean PTSD Checklist score of 37.4 (95% Confidence Interval = 34.0-40.7) and usual care patients demonstrated a mean PTSD Checklist score of 42.5 (95% Confidence Interval = 39.3-45.7).⁶⁷ Projecting these differences to the current investigation, with 20% 12-month attrition, 424 patients, the probability of a 2-tailed type I error set at 5%, correlation between observations of 0.7 and an anticipated effect size = 0.34, the power to detect differences in PTSD symptoms will be ≥ 0.80 .

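### PTSD Checklist model: leaving the arms' baseline means free costs some precision for no gain; a common baseline mean should be pre-specified

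*Combined protocol and SAP*

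**What the plan says.** Section VIII (Data Analyses, Overview) defines the dependent variables of the mixed models as "repeated measurements of the baseline, 1-, 3-, 6-, 9-, and 12-month outcome assessments". For every outcome, "the study team will first fit models containing only time categories, intervention, and intervention by time interactions". The estimand is then named: "The effect of major interest will be the time by treatment group interaction term".

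Covariates come later: "The impact of including covariates in the model will be examined in planned sensitivity analyses". A further clause reads "Any baseline injury, demographic, or clinical variables found to be statistically significant in this analysis will also be included as covariates in the regression models". The missing-data section adds predictors of attrition as covariates. None of these provisions names the baseline PTSD Checklist score, and nowhere does the plan set the arms' baseline means equal.

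On timing, section V (Inclusion Criteria) states "Prior to randomization, all patients will complete the full baseline assessment", and "patients who score ≥ 35 on the PTSD checklist and endorse ≥ 1 severe posttraumatic concern will be randomized". Table 1 shows the PTSD Checklist at baseline and at all five follow-up interviews.

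The power statement for this outcome (Sample Size and Power, iii) assumes 424 patients, 20% attrition at 12 months and a two-sided 5% test, with "correlation between observations of 0.7 and an anticipated effect size = 0.34, the power to detect differences in PTSD symptoms will be ≥ 0.80".

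**The concern.** With categorical time, an intervention main effect and their interaction, the model has a separate free mean for each arm at each of six occasions, baseline included. With baseline as the reference, the 12-month interaction equals the arm difference at 12 months minus the arm difference at baseline, and the other visits follow the same pattern. The test therefore compares change scores.

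In a randomised trial whose baseline is measured before allocation, both arms are samples from one population, so the second component has expectation zero. Subtracting its estimate leaves the target unchanged and usually adds variance. A model with one shared baseline mean, or one that conditions on the baseline score, uses the same data and in large samples is never less precise.

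At stake is the width of the confidence interval for one of the primary patient-reported outcomes, and some power.

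**Working it through.** **Inputs from the plan.** 212 per arm; 20% attrition, so 0.80 × 212 = 169.6 per arm at 12 months; standardised effect d = 0.34; correlation ρ = 0.7; two-sided 5%.

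**Assumptions.** The plan gives one correlation and does not say that it applies to the baseline/12-month pair. It gives no ratio of baseline SD to follow-up SD (k below). Both are therefore varied.

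**Step 1: the plan's own figure.** A plain two-group comparison at 12 months has power Φ(d·√(n/2) − 1.96). With d = 0.34 and n = 169.6, this is Φ(0.34 × 9.209 − 1.96) = Φ(1.17) = 0.879, which meets the stated floor of 0.80. The same formula at d = 0.26 gives 0.668, against the stated 0.67 for physical function. The stated figures are thus consistent with a 12-month comparison of follow-up scores, which uses neither baseline nor ρ.

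**Step 2: variances.** In units of 2σ²/n, where σ is the follow-up SD:

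- follow-up score only: 1
- free baseline means (change contrast): k² + 1 − 2ρk
- common baseline mean, or baseline as covariate: 1 − ρ²

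**Step 3: at the plan's ρ = 0.7 with equal SDs (k = 1).** Free: 2 × (1 − 0.7) = 0.60. Common: 1 − 0.49 = 0.51. The ratio is 0.60/0.51 = 1.18. A generalised least squares calculation for all six occasions, with assumed monotone dropout to 80%, gives 1/0.870 = 1.15. A 20,000-run simulation on complete data gives 1/0.850 = 1.18. Power is Φ(3.131/√0.60 − 1.96) = 0.981 against Φ(3.131/√0.51 − 1.96) = 0.992.

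**Step 4: range.**

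| ρ | k | Free | Common | Ratio | Power, free | Power, common |
|---|---|---|---|---|---|---|
| 0.7 | 1.0 | 0.60 | 0.51 | 1.18 | 0.981 | 0.992 |
| 0.7 | 0.8 | 0.52 | 0.51 | 1.02 | 0.991 | 0.992 |
| 0.5 | 1.0 | 1.00 | 0.75 | 1.33 | 0.879 | 0.951 |
| 0.5 | 0.8 | 0.84 | 0.75 | 1.12 | 0.927 | 0.951 |

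**Step 5: effect of the entry threshold.** Write b for the slope of follow-up on baseline, V_b for the baseline variance and V_res for the residual variance. The ratio is then 1 + V_b(1 − b)²/V_res. Under a linear regression with constant residual variance, selecting patients on baseline leaves b and V_res unchanged and reduces V_b, so the ratio falls. As an illustration, take equal SDs and ρ = 0.7 before selection, a normal baseline and a cut at its mean (the position of the cut is an assumption). V_b falls from 1 to 0.363, and the ratio from 1 + 0.09/0.51 = 1.18 to 1 + 0.363 × 0.09/0.51 = 1.06. Starting from ρ = 0.5, it falls from 1.33 to 1 + 0.363 × 0.25/0.75 = 1.12.

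**Step 6: joint test.** The plan does not say whether the interaction is tested jointly (5 df) or at one visit. Assuming compound symmetry, the same dropout and an effect growing linearly to 0.34, joint power is 0.990 against 0.995 at ρ = 0.7, and 0.895 against 0.945 at ρ = 0.5.

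**The case against.** The planned model is conventional and unbiased, and its type I error is correct. At the plan's own correlation it has more power than the follow-up-only comparison that reproduces the stated figures, and the alternative gains about one percentage point. The plan does not single out month 12, so the contrast above is only one reading of the interaction. All of this stands, and it limits the point to efficiency.

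Four stronger readings are tempting, and the documents do not support them.

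- *The trial is underpowered for PTSD symptoms.* With equal SDs, the 12-month contrast falls below 0.80 only if the baseline-to-12-month correlation is under about 0.37; with an SD ratio of 0.8, under about 0.24. The documents give no such values.
- *The entry threshold makes the loss worse by lowering the correlation.* It does lower the correlation, but it also lowers the baseline SD. Step 5 shows that the net effect is a smaller loss.
- *The planned contrast is worse than ignoring baseline.* This needs a low correlation together with similar SDs. At 0.3 with equal SDs, power would be 0.754 against 0.879 for follow-up scores alone. At the same correlation, power is 0.828 with an SD ratio of 0.8 and 0.879 with 0.6, where the disadvantage has gone. A restricted baseline spread cannot be used to argue for the low correlation while the SDs are held equal.
- *The covariate provisions already solve it.* They do not. The significance-triggered clause depends on the data and does not name the baseline score. Adding that score as a main effect while baseline stays in the response would not constrain the interaction.

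**Conclusion.** The point holds as a modest, avoidable loss of precision for the PTSD Checklist. The planned terms estimate a baseline difference that randomisation makes zero. At ρ = 0.7 with equal SDs, the 12-month contrast carries about 15 to 18% more variance than needed, for a power difference of about 0.98 against 0.99. With the baseline SD at 80% of the follow-up SD, the excess is about 2%. At an assumed ρ of 0.5 with equal SDs, it is 33%, with power 0.88 against 0.95.

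There is no bias, and no stated figure is shown to be wrong. The algebra is firm. The size depends on a correlation and an SD ratio that the documents do not give for this pair of visits.

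The result should not be carried over to the other patient-reported outcomes. Table 1 lists the SF-12 but not the SF-36 at baseline, and every patient enters with at least one severe concern, so that dichotomous outcome has no baseline variation.

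**What to change.** For the PTSD Checklist only, pre-specify one of two models:

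1. Keep baseline in the response with a mean common to both arms: no intervention term at baseline, arm-by-time terms at 1, 3, 6, 9 and 12 months, and an unstructured covariance.
2. Model the follow-up scores only, with baseline PTSD Checklist score by time as a covariate.

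In either case, report the adjusted arm differences at the follow-up visits as the treatment effect, and state whether the test is joint or at a named visit.

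The first option keeps every randomised patient with a baseline score in the likelihood and leaves the plan's missing-at-random approach intact. The cost is a PTSD-specific line of model wording and the matching code, with no new data. Physical function and concern severity need their own statement of how baseline is handled.

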Randomization. After completing the baseline assessment, subjects are randomized to one of two active comparator conditions. A total of 424 patients will be randomized to either receive surgical team notification to initiate a mental health consultation (n =212), or receive a peer-integrated collaborative care intervention (n =212). Randomization will occur in a 1:1 ratio according to a computer-generated random assignment sequence in blocks of either 4 or 6 patients, prepared by the study biostatistician. After a patient has been randomized, a member of the study team will return to the hospital as soon as feasibly possible to inform the patient if he/she has been randomly assigned to the enhanced usual care or intervention condition.

Blinded telephone follow-up interviews. Patient-reported outcomes will be assessed at 1-, 3-, 6-, 9- and 12 months after the injury event by telephone interview. Telephone interviews have been found to be reliable and valid in the assessment patient reported outcomes for injured trauma survivors.^{67,71,107} In order to minimize bias, the research assistants conducting the telephone follow-up interviews will be blinded to the patient's study group assignments (**IR-6**).

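### Extra covariates for the adjusted models are picked by testing baseline differences between randomised arms, so the content of the robustness check depends on chance imbalance rather than prognosis (minor)

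*Combined protocol and SAP*

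**What the plan says.** All of this is in the combined protocol and SAP.

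- **Models, in order (section VIII, Data Analyses).** For every outcome, "the study team will first fit models containing only time categories, intervention, and intervention by time interactions". On the estimand: "The effect of major interest will be the time by treatment group interaction term".
- **Covariates entered regardless.** "Important injury and demographic characteristics, such as Injury Severity Score and age, will be entered into the models as covariates in planned sensitivity analyses". The two variables are given as examples, so the list is open.
- **Covariates entered by test.** Before those analyses the team compares baseline characteristics between arms. It then adds the significant ones: "variables found to be statistically significant in this analysis will also be included as covariates in the regression models". The plan gives no candidate list and no threshold, and does not require a selected variable to predict outcome. The reason offered is that "it is essential to control for any known confounders in the design and analysis to prevent a biased assessment of the treatment effect".
- **A second data-driven route (section VIII, missing-data standards).** Factors found to explain missing data also become covariates in later analyses.
- **Allocation (section V, Randomization).** "Randomization will occur in a 1:1 ratio according to a computer-generated random assignment sequence in blocks of either 4 or 6 patients". The baseline interview is completed before randomisation.

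**The concern.** Under valid randomisation, a baseline difference between arms is a chance event, whatever its p-value. A significance test of that difference says nothing about whether the variable predicts outcome. A strong predictor that is not one of the named examples enters as rarely as an irrelevant variable. The stated aim, control of confounding, is not served by a rule that ignores the link with outcome.

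The adjusted analysis is there to show whether the main result is robust. As written, its content is known only after baseline data have been compared by arm. It also depends on which variables are tested and at what level. Two analysts who both follow the text could report different adjusted models.

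**Working it through.** **1. Reproduce the plan's own figure.** The rule changes no stated power, but one figure fixes the scale. The physical function item under Sample Size and Power gives effect size 0.26, 424 patients, 20% attrition, two-sided 5% and power of at least 0.67.
- Evaluable per arm: 212 × 0.8 = 169.6.
- Power = Φ(d√(n/2) − 1.96) = Φ(0.26 × √84.8 − 1.96) = Φ(2.394 − 1.96) = 0.668. This agrees.

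**2. Chance entry.** Assumptions not in the documents: tests at 5%, independent, k variables tested. P(at least one enters) = 1 − 0.95^k.
- k = 10: 0.40
- k = 20: 0.64
- k = 30: 0.79

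Any single variable enters about 5% of the time. With 18 variables tested, a simulated prognostic variable entered in 4.5% to 5.7% of trials.

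**3. Type I error.** In simulation under the rule (170 per arm, two covariates always in, 18 tested) it was 0.041 to 0.052 over five settings. With a single tested covariate at 212 per arm it was 0.050, 0.044 and 0.038 at covariate–outcome correlations r of 0.3, 0.5 and 0.7. There is no inflation.

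**4. The time-by-treatment test.** A baseline covariate entered as a main effect in a linear model shifts all of a patient's visits equally. With complete data it drops out of the within-patient contrasts that make up the arm-by-time term. That test is the same with or without the covariate.

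**5. Between-arm contrast, continuous outcome, baseline outcome not in the model.** 170 per arm, d = 0.26; r is assumed. Power = Φ(d√(n/2)/√(1 − r²) − 1.96), with d√(n/2) = 0.26 × √85 = 2.397.
- Covariate left out: Φ(0.437) = 0.669.
- Covariate in, r = 0.3: Φ(2.397/0.954 − 1.96) = 0.710, a gain of 4 points.
- Covariate in, r = 0.5: Φ(2.397/0.866 − 1.96) = 0.790, a gain of 12 points.

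Simulated power (6,000 trials per setting, Monte Carlo standard error about 0.006):

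| Where the prognostic variable sits | Plan's rule | Fixed list |
|---|---|---|
| Named, r = 0.3 | 0.694 | 0.698 |
| Named, r = 0.5 | 0.776 | 0.777 |
| Outside, r = 0.3 | 0.661 | 0.707 |
| Outside, r = 0.5 | 0.670 | 0.781 |

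At d = 0.34 the outside-variable figures are 0.870 v 0.900 (r = 0.3) and 0.889 v 0.951 (r = 0.5).

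**6. The same contrast, conditioning on the baseline outcome.** The plan includes baseline among the repeated measurements and assumes correlation 0.7 between observations. Let q be the covariate's correlation with baseline. The residual variance is 1 − (0.49 + r² − 2 × 0.7 × r × q)/(1 − q²).
- Baseline only: 1 − 0.49 = 0.51, power Φ(2.397/0.714 − 1.96) = 0.919.
- q = r: residual variance 0.501 (r = 0.3) and 0.480 (r = 0.5), power 0.923 and 0.933. The gain is about 0.5 to 1.5 points.
- q = 0.7r: residual variance 0.486 and 0.436, power about 0.93 and 0.95.
- q = 0: residual variance 0.42 and 0.26, power 0.959 and 0.997. The gain is 4 to 8 points.

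**7. Emergency department (ED) use.** The sample size section gives "at 3-6 months post-injury, 30% of nurse notification patients versus 17% of care management patients had one or more emergency department visits" and, at 12 months, 30% "versus 22% care management (8% difference across groups"). Logistic model, 212 per arm, an assumed prior-use covariate of 50% prevalence outside the named ones, 3,000 trials per setting (standard error about 0.009), rule v fixed list:
- 30% v 22%: 0.462 v 0.472 (covariate odds ratio 2); 0.462 v 0.497 (odds ratio 4).
- 30% v 17%: 0.893 v 0.900; 0.887 v 0.912.

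The odds ratio 2 differences are within about one standard error of the simulation.

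**The case against.** The strongest defence is that the rule governs a sensitivity analysis. The unadjusted model is fitted first, covariates are placed in planned sensitivity analyses, and the significant variables are added alongside age and Injury Severity Score. That is the natural reading and it stands.

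A reader might infer more: that the adjusted model could become the main result, because the sentence refers to the regression models without restriction and control of confounders is called essential. The text leaves this loose, but nothing in it promotes the adjusted model. A reader might also infer a false-positive problem or a loss of planned power. Steps 3 and 4 show neither, and the power statements mention no covariates.

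Three further points also stand.
- The 12-point figure comes from a single-endpoint model without baseline and needs an unnamed covariate at r = 0.5, which the documents do not support. With baseline conditioned on, the gain may be a point or so.
- For ED use, baseline is among the listed measurements, so prior use may already be partly represented, depending on how baseline use is defined.
- The heterogeneity analyses already examine traumatic brain injury (TBI), gender and ethnic/racial status as main effects and interactions, though not in the adjusted sensitivity model.

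None of this defends choosing covariates by between-arm significance. It limits how much the choice matters.

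**Conclusion.** The point holds as a minor one. The plan states a rule that selects covariates on chance, and together with the open list of examples this leaves the adjusted sensitivity model undefined until the data are seen by arm. That weakens it as a check of robustness.

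The documents do not support a claim that the primary comparison is biased, that type I error rises, or that any stated power is wrong. The arm-by-time test is untouched in a linear complete-data model.

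The possible cost is precision in adjusted between-arm contrasts, and only where a prognostic variable lies outside those entered regardless:
- none if the prognostic variable is a named one;
- up to about 12 points without the baseline outcome (d = 0.26, r = 0.5);
- about 0.5 to 1.5 points with baseline conditioned on at 0.7 and equal correlations, more if the covariate correlates less with baseline;
- small for ED use, and partly within simulation error.

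The test level, number and independence of candidate variables, covariate correlations, and covariate prevalence and odds ratio are all assumptions.

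**What to change.** - Delete the significance-based entry rule and present baseline balance descriptively.
- Fix a short closed list of prognostic covariates already collected for the adjusted sensitivity model. Examples are age, Injury Severity Score, gender, TBI and, for ED use, pre-injury service use where the baseline measurement does not already carry it.
- State that the unadjusted time, arm and arm-by-time model is primary, and report both models for each outcome.
- Reconcile this with the missing-data standards: put covariates found to predict missingness in a separate, labelled missing-data sensitivity model, so that they do not reopen the closed list.
- Date the list. The section on additional COVID-19 exploratory analyses reports treatment-by-time models as already performed. If outcomes by arm had been seen when the list was set, say so and give the prognostic reason for each variable; the list could not then be called fully pre-specified.

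The cost is SAP text and a little more analysis; no new data are needed. In logistic models the adjusted odds ratio is conditional. In the 30% v 22% example it is 0.652 or 0.634 (covariate odds ratio 2 or 4), against a marginal (0.22/0.78)/(0.30/0.70) = 0.658. Marginal risk differences should therefore be reported as well.
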